**Outcome Definition, sample size justification, and analysis plans by objective/hypothesis**

**Objective 1:** To assess among HIV-infected individuals ages 40-75 sex-based differences in immune activation and statin-induced immunomodulation in relation to clinical CVD events.

***Hypothesis A)*** *Levels of immune activation markers will be higher in HIV-infected women versus men.* The outcome being tested in this sub-objective is baseline (pre-treatment) immune activation, as measured by the levels of each of select immune activation markers such as sCD14. A non-parametric alternative to t-test (eg, Mann-Whitney test) will compare the pre-treatment distribution of each biomarker between groups assigned by sex. If 22% female enrollment is achieved, then the comparison group sample sizes to address this hypothesis will be 1198 women versus 4248 men (with no adjustments for losses as outcome assessed at baseline). Using these sample sizes and the standard deviations of select biomarkers [Fitch 2013], and adjusting the significance level to 0.0167 by Bonferroni to account for the biomarkers being tested, there will be 90% power to detect sex differences of 214 ng/mL for sCD14. Covariate adjusted models performed as part of the analysis of this hypothesis will use multivariable regression (linear, with log transformation if indicated based on biomarker distribution).

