the outcome of MACE. To assess power for interaction effect, methods described in [VanderWeele 2012] will be used under the following assumptions: 4.9% of men with low immune activation will have a qualifying MACE outcome; the main effect odds ratios (OR) for sex and immune activation are each 2.1 (eg, 4.9% MACE in one group compared with 9.8% in the other); a multiplicative interaction OR of 1.33; association between sex and high/low immune activation of 1.33; and 22% female enrollment. Based on these assumptions and using a significance level adjusted to 0.0167, the statistical power for additive interaction effect (eg, as excess in relative risk attributed to interaction) is estimated as 80%. Testing for interaction effects and covariate adjusted models will use multivariable logistic regression (for the primary outcome) and Cox proportional hazards regression (for the secondary, time- to-event formulation outcome).

*Hypothesis C)* *Statins will decrease levels of immune activation markers to a greater extent in HIV-infected women versus men.* The outcomes being tested in this sub-objective are the changes from pre-treatment to 1 year of follow-up of the immune activation markers tested. For this hypothesis, statistical interactions of sex and treatment effects will be tested using linear (log transformed as indicated) models, which can also incorporate covariate adjustment. With estimates of 5% per year loss to follow-up, the effective sample size for this sub-aim is 5174 persons. For the biomarker sCD14, standard deviation of the outcome measure for this sub-aim is estimated assuming standard deviation of 1-year measurements same as baseline and intra-person correlation of 0.65. Further, assuming under additivity a 125 ng/mL effect of sex on sCD14 differences at 1 year and the same effect of statins on sCD14 differences at 1 year, there will be 80% power to detect an additive interaction effect of 220 ng/mL.

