outcome being tested in this sub-objective is baseline (pre-treatment) immune activation, as measured by levels of certain biomarkers such as sCD14. A non-parametric alternative to t-test (eg, Mann-Whitney test) will compare the pre-treatment distribution of each biomarker within women between groups assigned by menopause status. As per Objective 1A, 22% female enrollment is assumed. Further assuming a 1:1 ratio between female comparison groups, sample sizes for the pre-menopausal and post-menopausal groups will be 599 each. Using these sample sizes, standard deviations for biomarker as in Objective 1A, and Bonferroni-adjusting the significance level to 0.0167, there will be 90% power to detect differences between the pre- and post-menopausal groups of 378 ng/mL for sCD14. Alternatively, if the ratio between female comparison groups is 1:2, sample sizes for the pre-menopausal and post-menopausal group will be 399 and 799, respectively. Under this contingency, the minimal detectable differences between female comparison groups for 90% power are only slightly higher at 401 ng/mL.

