*Hypothesis C)* *Statins will decrease levels of immune activation markers to a greater extent in post-menopausal HIV-infected women versus pre-menopausal HIV-infected women.* The outcomes being tested in this sub-objective are the changes from pre-treatment to 1 year of follow-up of each of the immune activation markers tested parallel to Objective 1C. Interactions by menopause status and treatment will be tested using linear (log transformed as indicated) models, which can also incorporate covariate adjustment. Assuming a 22% female enrollment and a 5% per year loss to follow up, the effective sample size for this analysis is 1138. Assuming a 1:1 ratio of female comparison groups, the sample sizes will be 569 for the pre- and post-menopausal groups. Using analysis assumptions from Objective 1C, and under additivity assuming a 375 ng/mL effect of menopause on sCD14 differences at 1 year as well as a similar effect of statins on sCD14 differences at 1 year, there will be 80% power to detect an additive interaction of menopause and statin of 390 ng/mL.

Hypothesis D) CVD risk-reduction will be mediated in part through statin-induced immunomodulation, more so in post-menopausal (vs. pre-menopausal) HIV-infected women. Parallel to Objective 1D, the SEM model will be used to incorporate all biomarker data into a single model for CVD clinical outcome, and then to test the covariate pathways, including directionality and temporal ordering. For this sub-objective, some of these pathways to be tested include the following: direct effect of menopause status on CVD, direct effect of menopause status on immunomodulation, direct effect of immunomodulation on CVD, menopause effect on CVD through immunomodulation, direct effect of statin on CVD and on immunomodulation, and menopause effect on CVD through statin effect.

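### Appendix IV claims 80% power for the sex-by-statin and menopause-by-statin interactions on sCD14; the SD it implies and the assumptions it states give about 60–62% at two-sided 5% (68–70% with baseline adjustment)

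*Protocol*

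**What the plan says.** All of this is in Protocol Appendix IV, under the outcome definitions and sample size justification.

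- **Hypothesis 1C (sex by statin).** The outcome is change: "The outcomes being tested in this sub-objective are the changes from pre-treatment to 1 year of follow-up of the immune activation markers tested". Its SD is "estimated assuming standard deviation of 1-year measurements same as baseline and intra-person correlation of 0.65". After 5% loss the effective sample is 5174, and the claim is that "there will be 80% power to detect an additive interaction effect of 220 ng/mL".
- **Hypothesis 2C (menopause by statin).** It takes over the analysis assumptions of 1C, with 569 women in each menopause group, and claims that "there will be 80% power to detect an additive interaction of menopause and statin of 390 ng/mL".
- **Hypothesis 1A (baseline sex difference).** "the comparison group sample sizes to address this hypothesis will be 1198 women versus 4248 men"; at a Bonferroni level of 0.0167, "there will be 90% power to detect sex differences of 214 ng/mL for sCD14".
- **Hypothesis 2A (baseline menopause difference).** With 599 per group at 0.0167 and the same SD as 1A, there is "90% power to detect differences between the pre- and post-menopausal groups of 378 ng/mL for sCD14"; with 399 versus 799 the figure is 401 ng/mL.

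No SD for sCD14 is printed anywhere. Neither 1C nor 2C states alpha, sidedness or whether the entry value is a covariate. The appendix uses 0.0167 in 1A, 1B and 2A, and 5% in 2B. Section 9.6.1 of the main protocol sets two-sided tests at 5%.

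**The concern.** The missing SD can be recovered from the 90% power statements in 1A and 2A. Carried into 1C and 2C with the stated correlation, it gives a standard error too large for 80% power at the stated effects. The shortfall is in the same proportion in both hypotheses.

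These two tests address ancillary objective 1.2.3.1, whether sex and reproductive ageing modify the statin's immune effect. A non-significant interaction set against a stated 80% power suggests a type II error of 20% at the stated effect. On the change score at two-sided 5% it is nearer 40%.

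**Working it through.** **Step 1: reproduce the 90% statements and recover the baseline SD.** For a two-sample comparison, SD = d / [(z(1−0.0167/2) + z(0.90)) × √(1/n₁ + 1/n₂)], and the two normal quantiles sum to about 3.675.

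- 1A: 214 / (3.675 × √(1/1198 + 1/4248)) = 1780
- 2A, 1:1: 378 / (3.675 × √(2/599)) = 1780
- 2A, 1:2: 401 / (3.675 × √(1/399 + 1/799)) = 1780

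Run forward, an SD of 1780 returns 90.0% power in all three. If the planners allowed for the Mann-Whitney test's efficiency of 0.955, the underlying SD is 1780 × √0.955 = 1740.

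**Step 2: SD of the stated outcome.** With equal SDs at both times and correlation 0.65, SD(change) = 1780 × √(2 × (1 − 0.65)) = 1489. With the entry value as covariate, the residual SD is 1780 × √(1 − 0.65²) = 1353.

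**Step 3: standard error of the interaction.** Treatment is 1:1 (section 9.3), so SE = SD × √(4/nA + 4/nB).

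- 1C: 22% of 5174 gives 1138 women and 4036 men. SE = 1489 × √(4/1138 + 4/4036) = 100.0
- 2C: 569 per group. SE = 1489 × √(8/569) = 176.6

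**Step 4: power = Φ(δ/SE − z).** At two-sided 5%:

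- 1C: Φ(220/100.0 − 1.96) = 59.5%
- 2C: Φ(390/176.6 − 1.96) = 59.8%

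The claimed 80% is not reproduced. The main effects of 125 and 375 ng/mL assumed in the appendix do not enter the variance of the interaction contrast. Unequal sex groups are not the cause either, because 2C is balanced and falls short equally.

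**Step 5: other settings.**

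| Setting | 1C, 220 ng/mL | 2C, 390 ng/mL |
|---|---|---|
| Change score, two-sided 5%, SD 1780 | 59.5% | 59.8% |
| Change score, two-sided 5%, SD 1740 | 61.5% | 61.8% |
| Entry value as covariate, two-sided 5%, SD 1780 | 67.8% | 68.1% |
| Entry value as covariate, two-sided 5%, SD 1740 | 69.8% | 70.1% |
| Change score, two-sided 0.0167, SD 1780 | 42.4% | 42.7% |
| Change score, two-sided 0.0167, SD 1740 | 44.4% | 44.7% |
| Change score, one-sided 5%, SD 1780 | 71.1% | 71.4% |
| Entry value as covariate, one-sided 5%, SD 1780 | 78.2% | 78.4% |
| Entry value as covariate, one-sided 5%, SD 1740 | 79.8% | 80.0% |

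Even at the lower bound of rank-test efficiency, 0.864 (SD 1655), two-sided 5% gives about 66% for the change score and 74% with the covariate.

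**Step 6: what 80% would require at two-sided 5%.** The detectable interaction is (1.96 + 0.84) × SE.

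- Change score, SD 1780: about 280 ng/mL (1C) and 495 ng/mL (2C), some 27% above the stated effects.
- Entry value as covariate (SEs 90.8 and 160.4): about 254 and 449 ng/mL.
- Alternatively, keeping 220 and 390 ng/mL with the change score would need a correlation of about 0.78, not 0.65.

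**The case against.** The strongest reply is that the appendix leaves enough unsaid for 80% to be reachable without any error. The SD comes from a cited cohort and is not shown. Both hypotheses are directional, and the linear models in 1C and 2C may take covariates. An SD of 1740, the entry value as covariate and a one-sided 5% test give 79.8% and 80.0%, very close to what is printed. That stands as a reason not to claim to know how the figures arose. It does not rescue them as written: the combination contradicts the two-sided rule in section 9.6.1, and it replaces the SD of the change, which 1C names as its outcome, with a residual SD.

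A reader might infer that the SD was multiplied by 0.65 instead of √0.7. That does give 80.9% and 81.1%, but the documents do not show it. The one-sided combination above matches the printed effects more closely: it gives detectable effects of about 221 and 390 ng/mL, against about 218 and 384 ng/mL for the supposed slip.

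A reader might also infer that power is simply 42%. That holds only if the Bonferroni level applies to 1C and 2C. Neither states it, and 2B in the same appendix uses 5%.

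Two further points stand in part. First, the appendix's 5446 participants predate the increase from 6500 to about 7500. If that number scaled with enrolment at 22% women (an assumption), two-sided 5% power would be about 66% for change scores and 74% with the covariate, still below 80%. Second, no sample size, stopping rule or main endpoint depends on these figures, and confidence intervals for the interactions would show the precision achieved.

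**Conclusion.** The point holds in this form. On the appendix's stated correlation and sample sizes, and the SD implied by three of its own figures, power for the 220 and 390 ng/mL interactions is about 60–62% with the change score and 68–70% with the entry value as covariate, not 80%. None of the settings examined that keep the two-sided 5% rule and the variance implied by the stated correlation reaches 80%.

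The conclusion rests on an inferred SD (1780, or 1740 allowing for the rank test), on 1:1 treatment within each subgroup, and on section 9.6.1's two-sided 5% level governing these tests. The 42–45% figure is conditional on alpha being 0.0167. The cause of the discrepancy is not established. These are ancillary hypotheses, so the point says nothing against the power for MACE. It is a correction worth making because a stated power is wrong and putting it right is cheap.

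**What to change.** In Appendix IV, Hypotheses 1C and 2C:

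1. Correct the power statements. On the present sample sizes at two-sided 5%, give the interactions detectable with 80% power as about 280 and 495 ng/mL for change scores, or about 254 and 449 ng/mL with entry sCD14 as covariate. Re-derive them if the sample size is updated for the enlarged trial.
2. Print the SD used for sCD14, and state alpha (0.05 or 0.0167), sidedness and the model assumed.
3. Pre-specify entry sCD14 as a covariate. The linear models in both hypotheses already allow this, and it raises power from about 60% to 68% at the same SD.

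The cost is wording and a less favourable stated figure. No participants, visits or assays are added.

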## APPENDIX IV: REPRIEVE OBJECTIVES TO DECIPHER SEX-SPECIFIC MECHANISMS OF CVD RISK AND RISK REDUCTION

### BACKGROUND

HIV-infected individuals face a markedly increased risk of cardiovascular disease (CVD), even when viremia is suppressed by combined antiretroviral therapy (cART) [Freiberg 2013; Triant 2007]. Mechanisms underlying HIV-associated CVD risk are incompletely understood [Zanni 2014] and specific guidelines on cardioprotective care for this population are not available [Stone 2014]. Characterizing and reducing CVD risk among HIV-infected women represents a particular challenge. HIV-infected women are less likely than HIV-infected men to be offered preventive cardiac care in clinical practice [Willig 2008]. However, data suggest women with HIV are just as likely as their male counterparts to incur an MI [Triant 2007]. Indeed, a large-scale US epidemiologic study shows that among HIV-infected women, unadjusted rates of MI modestly exceed those among HIV-infected men [Triant 2007]. Moreover, the same study reveals a significantly higher adjusted relative risk of MI in HIV infected-women versus uninfected females (2.89) as compared with HIV-infected men versus uninfected males (1.4) [Triant 2007]. The proposed objectives aim to identify sex-specific mechanisms of CVD risk and risk reduction in relation to adjudicated clinical CVD events in HIV. Immune activation is increased in HIV-infected women (versus HIV-infected men) [Fitch 2013] and especially among those HIV-infected women who have undergone menopause [Looby 2015]. Moreover, among women with HIV, reduced ovarian reserve has been shown to relate to subclinical atherosclerotic plaque even after controlling for traditional CVD risk factors, including age [Looby 2015]. Building on these observations, our aims interrogate immune and hormonal pathways hypothesized to contribute to CVD risk in HIV-infected women across the reproductive aging spectrum.

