## STATISTICAL CONSIDERATIONS

### Overview Considerations

Overall sample size assumptions: The projected sample size is 5446 persons, or approximately 80% of the total REPRIEVE study sample.

General analysis plans: As comparison groups to address the objectives listed below (eg, groups classified by sex for Objective 1 and by menopause/hormone status for Objective 2) will not have been assigned by randomization, the distributions of baseline characteristics will be compared between groups to help inform the list of characteristics to be included in covariate

.adjusted models specified below. Baseline covariates anticipated to differ by sex (eg, race, hypertension, smoking, substance use, lipids, BMI) [Hattleberg 2014] will be carefully explored and considered, particularly when they are hypothesized to be prognostic for the outcome. Where treatment effect is included in the analysis plan below (eg, statin effect), this variable will use intent-to-treat formulation.

**General monitoring considerations:** Safety of human participants participating in the objectives described will be monitored by the REPRIEVE DSMB as part of the REPRIEVE trial study monitoring plan.

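### The only test written for Hypothesis 2A in Appendix IV is an unadjusted rank test, with no age-adjusted model, so a menopause difference in immune markers could reflect age

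*Protocol*

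**What the plan says.** Appendix IV, Objective 2, covers women aged 40 to 75, classed as pre- or post-menopausal from hormone data and menstrual history. Hypothesis A is that post-menopausal women have higher baseline levels of markers such as sCD14. The test is stated once: a rank test of the Mann-Whitney type "will compare the pre-treatment distribution of each biomarker within women between groups assigned by menopause status".

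The power statement belongs to that two-group comparison. With a 1:1 split, "sample sizes for the pre-menopausal and post-menopausal groups will be 599 each", and at a Bonferroni-adjusted level of 0.0167 "there will be 90% power to detect differences between the pre- and post-menopausal groups of 378 ng/mL for sCD14". With a 1:2 split, "sample sizes for the pre-menopausal and post-menopausal group will be 399 and 799, respectively", and the detectable difference becomes 401 ng/mL.

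The overview under Statistical Considerations in Appendix IV recognises that the comparison groups of both objectives, including the menopause groups, are not randomized. Baseline characteristics are to be compared between groups to help choose covariates for adjusted models set out later in the appendix. The covariates it gives as examples are those expected to differ by sex: race, hypertension, smoking, substance use, lipids and BMI.

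Adjusted models then appear under Hypotheses 1A, 1B and 2B. For Hypothesis 2C, "Interactions by menopause status and treatment will be tested using linear (log transformed as indicated) models, which can also incorporate covariate adjustment". Under 2A there is none.

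**The concern.** In women aged 40 to 75, post-menopausal women will on average be older than pre-menopausal women. If a marker rises with age for any reason, an unadjusted comparison by menopause status will show a difference even when menopause contributes nothing. Objective 2 is about menopause status and ovarian reserve, so a reader of a significant 2A result will take it as a finding about menopause. The analysis as written cannot tell the two explanations apart.

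The detectable difference also describes the unadjusted contrast. The plan gives no figure for the contrast that holds age constant, which is estimated less precisely whenever age explains more of menopause status than of the marker.

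**Working it through.** **Inputs from Appendix IV.** 599 per group (1:1) or 399 and 799 (1:2); alpha 0.0167; power 90%; the sCD14 SD is taken as in Objective 1A but not printed. Objective 1A gives 214 ng/mL detectable with 1198 women and 4248 men at the same alpha and power. Two-sided testing comes from the General Analysis Considerations of the main protocol (section 9.6.1).

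**Step 1: recover the SD.** z(1 − 0.0167/2) = 2.393 and z(0.90) = 1.282, sum 3.675. SD = 214 / [3.675 × √(1/1198 + 1/4248)] = 1780 ng/mL.

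**Step 2: reproduce the plan's figures.**
- 1:1: SE = 1780 × √(2/599) = 102.9; 3.675 × 102.9 = 378 ng/mL.
- 1:2: 3.675 × 1780 × √(1/399 + 1/799) = 401 ng/mL.

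Both match, with power 90.0%. Allowing for the rank test's efficiency of 0.955 under normality gives 88.5% at 378 ng/mL.

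**Step 3: adjust for age.** Let R² be the share of variance in menopause status explained by age. The documents do not give it, so it is varied. The SE of the menopause coefficient is multiplied by √[1/(1 − R²)], with the residual SD left at 1780. Detectable difference = 378/√(1 − R²). Power at 378 = Φ[3.675 × √(1 − R²) − 2.393].

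| Assumed R² | Detectable at 90%, 599 per group (ng/mL) | Power at 378 ng/mL |
|---|---|---|
| 0.05 | 388 | 88% |
| 0.15 | 410 | 84% |
| 0.20 | 423 | 81% |
| 0.30 | 452 | 75% |
| 0.40 | 488 | 67% |
| 0.50 | 535 | 58% |

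For the 1:2 split, 401/√(1 − R²) gives 435 ng/mL at R² = 0.15 and 567 ng/mL at R² = 0.50. If age also explains some marker variance the loss is smaller: at R² = 0.30, with 5% of marker variance explained by age, power is 78% instead of 75%.

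**Step 4: rejection by the unadjusted test when menopause has no effect.** For a 1:1 split, an age-marker correlation r produces a group difference of 2 × r × √R² × SD. Example: r = 0.10 and R² = 0.50 give 2 × 0.10 × 0.707 × 1780 = 252 ng/mL. The rejection probability is close to Φ(252/102.9 − 2.393) = Φ(0.06), or 52%.

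| Assumed R² | r = 0.05: difference, rejection | r = 0.10: difference, rejection |
|---|---|---|
| 0.15 | 69 ng/mL, 4% | 138 ng/mL, 15% |
| 0.30 | 98 ng/mL, 7% | 195 ng/mL, 31% |
| 0.50 | 126 ng/mL, 12% | 252 ng/mL, 52% |

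The nominal rate is 1.67%.

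**The case against.** The strongest reply is that the overview already provides for this. It names menopause status among the non-randomized groupings and says observed baseline differences will guide the covariates. An age difference large enough to matter would show up at that step, and the listed examples concern sex, so the absence of age there says little about menopause. This stands in part: a reader might infer that the plan ignores adjustment in Objective 2, and it does not. But the overview relies on models specified under each hypothesis, and 2A has none. A covariate list chosen from observed imbalance is also not a commitment to age.

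It can also be said that 2A is worded as an association and that Objective 2 sets out to characterize relationships, so a raw difference is a legitimate quantity. That is fair, and a reason to keep the rank test as a description. It does not support interpreting the difference as due to menopause.

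Four stronger readings are tempting and not supported:
- **That the 90% power is an error.** Both 378 and 401 ng/mL reproduce for the test described.
- **That the background commits 2A to age control.** The result there that held "even after controlling for traditional CVD risk factors, including age" concerns ovarian reserve and coronary plaque. The background's statement on immune activation after menopause makes no such claim.
- **That one replacement detectable difference can be given now.** The documents contain no age distribution for the women, so any narrow figure rests on assumed ages.
- **That 2C is wrong for lack of an age-by-statin term.** Its models already allow covariates, and no size has been worked out for that interaction.

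**Conclusion.** The point holds as a gap in specification. Hypothesis 2A has a single, unadjusted test in women aged 40 to 75. The adjusted model that the overview leads the reader to expect is missing, and age is not named, so a significant result could be due to chronological age.

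The direction is clear; the size depends on two quantities the documents do not supply. For R² of 0.15 to 0.50, an age-sCD14 correlation of 0.10 gives about 15% to 52% rejection with no menopause effect, and a correlation of 0.05 about 4% to 12%. Over the same R² range the age-adjusted 90% detectable difference is about 410 to 535 ng/mL, and power at 378 ng/mL about 84% to 58%. At R² of about 0.05 or less, power stays within two points of 90%. These figures assume a 1:1 split, normal approximations and the back-solved SD of 1780 ng/mL.

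This is one hypothesis in an ancillary appendix and does not touch the trial's primary analysis.

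**What to change.** In Appendix IV, Objective 2, Hypothesis A:
- Make the main analysis a linear regression of the marker (log-transformed if needed) on menopause status, with age as a continuous, flexible term.
- Examine the estimate within the age range where pre- and post-menopausal women overlap. Few of the oldest women will be pre-menopausal, and outside the overlap the estimate rests on extrapolation.
- Keep the Mann-Whitney comparison as descriptive.
- Leave the 378 and 401 ng/mL statements in place, labelled as unadjusted. Beside them give the age-adjusted detectable difference with its assumed R², to be fixed from the observed ages.

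In Hypothesis C, a model adding age and age-by-statin would be a reasonable supportive analysis; it is optional.

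The cost is a few sentences in the appendix, a wider estimate and a less favourable detectable difference. Age is already collected, so no new data or visits are needed.
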